4.6.7 Other Safety Assessments

Not Applicable.

5 INTERIM ANALYSIS

An interim analysis with the purpose of informing further development of the clinical programme, including but not limited to dose selection for Phase 3 may be conducted when at least 175 randomized participants have completed 12 weeks of treatment. The unblinded team would consist of members responsible for the unblinded analysis conduct and members of the Unblinded Review Committee (URC). The URC would review the results of interim analysis. Details will be described in a separate URC charter.

7 APPENDIX

7.1 Appendix A Missing data handling: MI-RD and placebo-washout imputation

For post-baseline missing values on secondary endpoints used to assess Objective 2a and 2d ([Table 8](#)), a distinction in the imputation will be made between non-monotone and monotone missing data.

The steps of the imputation algorithm are described in [Table 12](#).

Table 12 - MMRM Missing Data Imputation Algorithm

Step	Description	
Step 1	Impute non-monotone missing data	Impute all non-monotone missing data using the Markov chain Monte Carlo (MCMC) method assuming missing data are missing at random (MAR). This is performed using PROC MI in SAS, stratified by treatment group, with the IMPUTE=MONOTONE and CHAIN=MULTIPLE options in the MCMC statement. The imputation model will include the baseline value of the respective secondary endpoint, along with all scheduled post-baseline assessments for that endpoint, organized in chronological order. In this step, 1000 imputation datasets will be generated using the seed 230612, each of which will now solely contain missing data of the same monotone pattern.
Step 2	Impute monotone missing data	
For each of the 1000 imputed datasets, impute all monotone missing values prior to the first occurrence of any of the intercurrent events described in the CSP for the respective secondary endpoint, assuming missing at random, using the MAR statement.
 
For each of the 1000 imputed datasets, impute all monotone missing values after the first occurrence of any of the intercurrent events described in the CSP for the respective secondary endpoint sequentially using the pattern mixture model assuming missing data are missing not at random (MNAR) with the seed 2306121. The preferred method of imputation will be to use MI-RD, where imputation of missing data will be performed after stratifying for each combination of treatment group and on-treatment status. To

		
impute missing data at Time t, participants are categorised either as on-treatment (= participant for whom Time t is during the on-treatment period), or as treatment discontinuers (= participant for whom Time t is outside the on-treatment period). Values after death ICE will not be imputed.
 
The pattern mixture model imputation with a predictive mean matching model is performed using PROC MI in SAS with the MONOTONE statement set to the REGPMM option. The statement is repeated sequentially for each measured timepoint, including baseline value and all previous timepoints. Participants who had missing data imputed at previous timepoints will contribute to the imputation for the current timepoint.

Step 3	Fit MMRM or ANCOVA models	
Fit the pre-specified MMRM model to each imputed dataset, each now without any missing data, using PROC MIXED and store the 1000 resulting least square mean estimates for each treatment group and the difference between treatment groups, and corresponding standard errors for each model.
 
If the MMRM model cannot be fitted due to convergence issues, use the ANCOVA model in this step.

Step 4	Pool MMRM or ANCOVA model estimates	
Pool results using Rubin's rules in PROC MIANALYZE in SAS to provide the final least square mean estimates, 95% CIs, and p-value for the difference between treatment groups.
 
In case in the pooling step zero between imputation variabilities are encountered when using the MMRM model, ANCOVA model may be considered.

This MI-RD approach described in Step 2 in [Table 12](#) will be used as long as the number of retrieved dropouts for each combination of treatment group and on-treatment status is sufficient to construct imputation models. The distribution of missing data, number and proportions, according to each missing data pattern will be summarised per treatment group.

If MI-RD cannot be used due to an insufficient number of retrieved dropouts, monotone missing data until Week 12 in the placebo group will be replaced based on participants in the same group using standard MI and assuming missing at random, including baseline value and observations between baseline and Week 12 in the imputation model. Missing values in the active treatment group after first occurrence of any of the intercurrent events described in the CSP will be replaced by washout multiple imputation. For the sensitivity analysis described in Section 4.2.2.5.1, all monotone missing values would be imputed with placebo washout if MI-RD is not feasible.

In washout multiple imputation, monotone missing data are imputed based on observed values in the placebo group only, including baseline value in the imputation model but not accounting for any observations after baseline. A total of 1000 datasets will be imputed. The seed for imputing non-monotone missing data will be the same as in the MI-RD analysis (i.e., 2306121). For the imputation of monotone missing data, seed 102010 will be used for the placebo group and seed 201020 will be used for the AZD0780 group.

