3.3.1.4 Intercurrent Events

Intercurrent events (ICEs) are events that happen after treatment initiation and affect either the existence or interpretation of planned measurements.

The intercurrent events, and the applied analysis strategy considered in this SAP are summarized in Table 3.

Table 3– Expected ICEs and the Corresponding Statistical Considerations by Estimand

ICEs	Hypothetical strategy for ICEs defined in the CSP	Treatment policy strategy for ICEs defined in the CSP	Handling in the safety analysis	
			On-treatment	On-study
1. Premature and permanent discontinuation of study treatment	Hypothetical strategy	Treatment policy strategy	Hypothetical strategy	Treatment policy strategy
2. Change in background lipid lowering statin therapy	Hypothetical strategy	Treatment policy strategy	Treatment policy strategy	
3. Initiation, change or discontinuation in non-prohibited background lipid lowering non-statin therapy	Hypothetical strategy	Treatment policy strategy	Treatment policy strategy	
4. (a) Prohibited medication affecting lipid parameters	Hypothetical strategy	Treatment policy strategy	Treatment policy strategy	
(b) Prohibited medication not affecting lipid parameters	Treatment policy strategy		Treatment policy strategy	
5. Any concomitant medication not explicitly specified in the above categories	Treatment policy strategy		Treatment policy strategy	

6. Death	Hypothetical strategy	Hypothetical strategy	Hypothetical strategy	Hypothetical strategy
----------	-----------------------	-----------------------	-----------------------	-----------------------

ICEs – Intercurrent Events

The occurrence of any ICE does not automatically trigger premature and permanent study discontinuation as described in Section 7. of the latest approved CSP. In case of still applying consent, the participants are expected to attend assessments as described in the Schedule of Activities.

The following ICEs are considered:

1 Premature and permanent discontinuation of study treatment

2 Change in background lipid lowering statin therapy

The allowed background lipid lowering statin therapies are described in Appendix F of the last approved version of CSP and the latest approved version of the Statin eligibility memo. Background therapy is recorded in the EDC as prior medication.

Possible mechanisms of change in background lipid lowering statin therapy include:

(a) Discontinue statin therapy

(b) Change to a different statin therapy in the same intensity category

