4.2.2.3 Handling of Dropouts and Missing Data

Monotone missing values will be imputed using different methods depending on whether they occurred prior to or after any of the ICEs described in the CSP (i.e., ICE 1, 2, 3, 4(a) described in [Table 3](#)). Details on the imputation algorithm is outlined in [Appendix A](#) [Missing data handling: MI-RD and placebo-washout imputation](#).

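### The fallback washout imputation is triggered by any protocol ICE, not only by stopping drug, so some active-arm participants still taking AZD0780 are imputed from placebo

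*SAP*

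**What the plan says.** SAP Appendix A (7.1) covers missing post-baseline values in the treatment-policy secondary analyses: Objective 2a (LDL-C) and Objective 2d (other lipids and hsCRP). Monotone missing values after an intercurrent event (ICE) can go down one of two branches.

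- **Preferred branch, MI-RD (Table 12, Step 2).** Here "imputation of missing data will be performed after stratifying for each combination of treatment group and on-treatment status". Status is judged separately at each time point, and the model uses baseline and all earlier time points.
- **Fallback.** It applies under this condition: "If MI-RD cannot be used due to an insufficient number of retrieved dropouts". For the active arms the rule is then "Missing values in the active treatment group after first occurrence of any of the intercurrent events described in the CSP will be replaced". The replacement method is washout, where each value is "imputed based on observed values in the placebo group only, including baseline value in the imputation model but not accounting for any observations after baseline". Missing placebo-arm values are imputed under MAR within the placebo arm, using baseline and later observations.

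SAP 4.2.2.3 identifies the events as "ICE 1, 2, 3, 4(a) described in" Table 3: (1) stopping study drug for good; (2) a statin change; (3) starting, changing or stopping ezetimibe or bempedoic acid; (4a) a prohibited drug that affects lipids. SAP 3.3.1.4 adds: "The occurrence of any ICE does not automatically trigger premature and permanent study discontinuation". SAP 3.3.1.3 closes the on-treatment period 10 days after the last dose or at the end of the on-study period, whichever comes first.

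**The concern.** Washout imputation describes someone whose study drug has worn off. That is a reasonable assumption after ICE 1. It does not fit ICEs 2, 3 and 4(a) on their own, because these are changes in other lipid drugs and do not end AZD0780 treatment. SAP 4.2.2.1 asks for the effect whatever happens to background therapy. For a participant still taking AZD0780, the value wanted is an on-drug value under the altered background.

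The fallback sets no condition on treatment status. Such a participant gets a placebo draw, and their own on-drug measurements play no part. Two things are at stake. The active-arm estimate is pulled toward placebo, and the same participant is handled differently depending on which branch is used. That choice rests on whether retrieved dropouts are judged sufficient, for which the SAP gives no number.

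**Working it through.** **1. The plan's own figure, and whether the fallback could be used.** Protocol 9.2 randomises about 375 and assumes about 15% discontinuation. 375 × (1 − 0.15) = 318.75, and 318.75 / 5 = 63.75 per arm, which reproduces the stated 320 and 64. The expected loss is 75 × 0.15 = 11.25, about 11 per arm. Protocol 7.1 sends those who stop drug to an early discontinuation visit and then Visit 8, while also asking that they stay in the study if possible. Week 12 values after stopping drug may therefore be few, and the fallback is a real possibility. The shortage would lie in the discontinuer cells. The on-treatment cells would still have roughly 64 potential donors per arm.

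**2. The two branches side by side**, for a monotone missing value after ICE 2, 3 or 4(a):

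| Participant at the missing time point | MI-RD | Fallback as written |
|---|---|---|
| Active arm, within on-treatment period | On-treatment participants of same arm; baseline and earlier values | Placebo; baseline only |
| Active arm, outside on-treatment period | Discontinuers of same arm | Placebo; baseline only |
| Placebo arm | Placebo arm, by treatment status | Placebo arm under MAR; baseline and later values |

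The first row is the problem: the fallback drops a split that can still be supported by data.

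**3. Who falls in the first row at Week 12.** The target day is 85. To be on treatment then, the last dose plus 10 days must reach Day 85, so the last dose is on Day 75 or later, and the participant must still be on study. Someone who changes statin and leaves on Day 57 is on treatment until Day 67 at the latest (57 + 10). At Week 12 MI-RD also classes that person as a discontinuer.

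The value must also be monotone missing. SAP 4.2.1.3 reserves that term for missingness with no later observation. LDL-C is measured again at Visit 8 (Day 99), and Table 12 Step 1 refers to all scheduled post-baseline assessments. On that reading, a missed Week 12 followed by an attended Visit 8 is non-monotone and is imputed under MAR in the participant's own arm. SAP 4.2.2.2 limits the analysed visits to 3 to 7. On that reading the same value is monotone and goes to washout. The SAP does not settle this.

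**4. Size.** If *k* of 75 participants in an arm are in the first row at Week 12, then

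shrinkage = (*k* / 75) × effect,

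where the effect is the gap between on-treatment and placebo values in percentage points. The planned effect is redacted, so 30 to 60 is assumed: 50 and 60 are the figures Protocol 2.3.2 gives for other PCSK9 agents, and 30 is an assumed lower bound. The documents do not give *k*; the columns are illustrations.

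| Assumed effect | k = 1 | k = 4 | k = 8 |
|---|---|---|---|
| 30 | 0.40 | 1.60 | 3.20 |
| 50 | 0.67 | 2.67 | 5.33 |
| 60 | 0.80 | 3.20 | 6.40 |

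**5. Simulation check** of the Week 12 mean difference. Assumptions: effect −50, SD 25, 75 per arm, four further active participants off drug with placebo-like values, no baseline covariate.

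| k | Truth | As written | Washout only off treatment |
|---|---|---|---|
| 1 | −47.30 | −46.62 | −47.28 |
| 4 | −47.38 | −44.70 | −47.36 |
| 8 | −47.25 | −41.95 | −47.28 |

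The gaps between truth and the rule as written (0.68, 2.68, 5.30) match the formula (0.67, 2.67, 5.33). The simulation assumes that the event itself does not change LDL-C, so the agreement in the last column follows partly from that assumption.

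**The case against.** The strongest case for leaving the rule alone has four parts.

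- **Narrow reach.** This is a fallback for secondary analyses whose p-values are nominal (SAP section 2). The primary analysis uses no explicit imputation (SAP 4.2.1.3). This stands.
- **Few participants.** Protocol 5.1 and 6.9 call for no planned medication change and stable lipid therapy, and step 3 above narrows the group further. Zero or one per arm is plausible. This stands, although the documents give no count.
- **Conservative and visible.** The pull is toward no effect. For LDL-C, sensitivity analysis 2 (SAP 4.2.2.5.2) reruns the model without explicit imputation and would show an effect of washout. This stands in part. Sensitivity analysis 1 cannot help, because under the fallback it extends washout to all monotone missing values. Objective 2d has no sensitivity analysis (SAP 4.2.4.5).
- **The alternative is imperfect.** Imputing from on-treatment participants of the same arm does not condition on the background change. ICE 2 includes stopping the statin, and efficacy could then be overstated. This is true, but MI-RD already has the same limitation, and for someone still on drug a donor on drug is nearer the estimand than a placebo donor.

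Three stronger readings are tempting. A reader might infer that washout has nothing to do with stopping drug; in fact ICE 1 is one of the triggers, and washout is reasonable there. A reader might infer that the two branches disagree for everyone who leaves after a statin change; SAP 3.3.1.3 puts most of them outside the on-treatment period by Week 12. A reader might also suppose that 2% to 5% of an arm is affected, which at an assumed effect of 45 would cost 0.9 to 2.25 points (0.02 × 45; 0.05 × 45). Nothing in the documents supports that share.

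**Conclusion.** The point holds as a specification gap of small expected size. As written, the fallback imputes placebo values for participants who are within the on-treatment period after ICE 2, 3 or 4(a). This departs from the preferred branch and from the treatment-policy question, and lack of data does not justify it, because on-treatment donors would remain.

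One such participant per arm moves the Week 12 difference by less than one percentage point over the assumed effect range. Larger shifts need several such participants, and the documents give no ground to expect them. The conclusion rests on MI-RD being judged infeasible, on an arm of about 75, on the assumed effect, and on at least one participant being on treatment with monotone missing data at Week 12. No conclusion about the primary endpoint depends on it.

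**What to change.** In the fallback paragraph of SAP 7.1:

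- Apply washout only to active-arm monotone missing values at time points outside the on-treatment period defined in SAP 3.3.1.3.
- Impute missing values after ICE 2, 3 or 4(a) that lie within the on-treatment period from on-treatment participants of the same randomised arm, using baseline and earlier post-baseline values, as MI-RD does.

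The cost is one or two sentences before unblinding. The on-treatment flag is already derived for MI-RD, so no new data or derivation is needed. The small downside is that the imputation does not condition on the background-therapy change; the SAP can state this as a limitation shared with MI-RD. The same edit could say whether Visit 8 counts when a Week 12 value is classed as monotone missing, since that affects how many participants are concerned.

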7.2 Appendix B Region definition

Region	Country
Asia	Japan
Europe	Czech Republic
	Denmark
	Hungary
	Slovakia
	Spain
North America	Canada
	United States of America
